#### 7.B.3.2. Description at Selection and during the Run-In Period

At Selection (*Visit 0*) and during the *Run-In Period (up to the end of Visit 1)*,

- patients' background, demographic data, social conditions,
- characteristics of the study disease, (*including GOLD stages classification and combined severity assessment classes as defined in section 3. separately*),
- need for oxygen therapy at Selection (*whatever its duration prescribed*) with its criteria for prescription and average daily duration prescribed,
- need for continuous Long Term Oxygen Therapy (*i.e., with daily oxygen duration prescribed of 15 hours or more*) at Selection,
- need for home Non-Invasive Ventilation (NIV) at Selection with its average daily duration prescribed,
- need for Continuous Positive Airway Pressure (CPAP) at Selection,
- smoking status and history,
- results of arterial or capillary blood gases,
- vital signs and pulse oximetry (*split by conditions of measurement: either on room air or on oxygen*) measurements,
- as well as the 6-minute walking distance and related parameters (*split by conditions of assessment: either on room air or on oxygen*),
- the patient's self-evaluations, the severity of dyspnoea,
- the Charlson Comorbidity Index score,
- the transthoracic Doppler echocardiography measurements,

- the clinical interpretation of a 12-lead ECG tracing,
- and the modalities of oxygen prescription, if applicable,

will be described by study group (*and globally*), on the Intention To Treat (ITT) data set (*defined in section 7.B.3.1*).

If a secondary PP data set is defined (*see section 7.B.3.1*) and if 10.0% or more of patients from the ITT data set are excluded from the PP data set, the description of patients by study group (*and globally*) at Selection and during the *Run-In Period (up to the end of Visit 1)* will be repeated on the PP data set, for all parameters apart from standard safety evaluation criteria.

At Visit 1, CRP, as well as haematology results will be tabulated by study group (*and globally*) as both quantitative parameters (*raw values converted in international units, if necessary*) and qualitative parameters (*relative positions regarding normal ranges in use in each laboratory involved*).

Results of the most recent pulmonary function tests performed in stable state prior to Selection, and results of the pulmonary function tests performed during the *Run-In Period* will be tabulated descriptively (*as both raw values and percentages of predicted values, when applicable*), by study group (*and globally*), together with the ratios FEV1/FVC and RV/TLC (*in the subgroup of patients for whom body plethysmography measurements at Visit 1 were collected*) as reported by the investigators in the electronic Case Report Forms.

No systematic statistical test will be performed to compare both groups of patients at Selection and during the *Run-In Period (up to the end of Visit 1)* on any data sets analysed. They will only be performed if any clinically significant imbalances between study groups appear to be of major importance for the interpretation of the primary efficacy criterion results and need to be cautiously examined in order to determine whether the randomisation has failed or not. If this descriptive analysis provides any clues on potential imbalances, further statistical investigations will be carried out using homogeneity tests and if necessary, the factor adjusting strategy will be redefined and the corresponding potentially predictive factor will be added to the ones pre-listed in section 7.B.3.5.

Concomitant diseases, as well as medical and surgical histories will be tabulated descriptively by study group (*and globally*) using the MedDRA codes of System Organ Classes and preferred terms.

All concomitant treatments with start date at the latest on the day preceding the patient's randomisation will be tabulated descriptively by study group (*and globally*) using the WHO-DRUG dictionary and the Anatomical Therapeutic Chemical (ATC) classification. Three (3) tables will be provided:

- one table showing the number and percentage of patients with at least one concomitant treatment with start date at the latest on the day preceding randomisation, by therapeutic area (*ATC1 code corresponding to ATC system main group*),
- one table by both ATC1 code and ATC system subgroup (*ATC2 code*),
- and one table showing the number and percentage of patients with at least one respiratory system concomitant treatment with start date at the latest on the day preceding randomisation, by ATC system subgroups (*ATC2, ATC3 and ATC4 codes*).

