## 7.B STATISTICAL METHODS

The primary analysis of the primary efficacy criterion is detailed in section 7.B.3.5. All other efficacy, safety and medico-economic statistical results provided will be exploratory and exclusively descriptive. They may not lead to any causal interpretation. As a consequence, the statistical significance level of the various two-sided tests performed will be 5.0%. No adjustment for multiplicity will be made.

At the end of the study, after the database lock, the statistical analysis will be performed by ITEC Services under the supervision of AIR LIQUIDE *Santé* INTERNATIONAL using the current version of the SAS® software, according to the statistical analysis plan approved after the medical and statistical review performed by the sponsor study personnel (*see section 4.B.4*).

Thorough description of all parameters reported will be presented separately by study group (*defined by the education program allocated to the patient at random, i.e., either the Intervention group or the Control group*), using the observed case approach. Summary tabulated results will be provided by study group and assessment time, if relevant or they will be replaced by the corresponding individual data listings if too few patients are concerned.

Quantitative parameters will be described using the following statistics: number of patients, mean, standard deviation, minimum, median and maximum values. Qualitative parameters will be described using frequencies and percentages and for binary variables, by their two-sided 95.0% confidence intervals of the observed rates (*assumed to be binomially distributed in both study groups*).

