- baseline Charlson Comorbidity Index (*which may be separated in a few appropriate categories prior to the exploratory research of its potential predictive role on the primary efficacy criterion*).

If the descriptive analysis of the comparability of study groups at Selection and/or during the *Run-In Period* reveals any random imbalance of clinical significance between both study groups (*as specified in section 7.B.3.2*), this list of a priori identified potentially predictive factors will be implemented accordingly.

To carry out the exploratory multiple-factor regression planned, the following analyses will be performed successively:

- in a first step, a two-factor regression analysis involving the study group and each of the investigated factor listed above separately, as well as their interaction will be performed. If some factors or their interaction appear to be predictive (*i.e., statistically significant at level  $\alpha = 0.10$* ) of the primary efficacy criterion, they will be gathered into a multiple-factor model in addition to the study group factor. Backward elimination at level  $\alpha = 0.10$  will then be applied for the model determination. Any factor remaining in the model will be considered an independent predictor,
- in a second step, an exploratory multiple-factor regression analysis involving the study group and all factors selected in the first step described above, including their interaction, if relevant, will be performed to identify the independent predictors of the primary efficacy criterion. Conclusions regarding the study group effect will be generalised if they apply to all subgroups based on other factors.

Goodness-of-fit (*i.e., predicted values are an accurate representation of the observed values*) of the final selected model will be investigated by providing summary measurements of the distance between observed and fitted values. Moreover, an analysis of the residuals of the final selected model will be performed (*using both Pearson's and deviance residuals*).

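### Homogeneity tests on noticed imbalances cannot show whether the randomisation failed, and should not decide which factors enter the exploratory regression

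*Protocol*

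**What the plan says.** Protocol 7.B.3.2 starts from the right rule: no systematic test of the two groups at Selection or during the Run-In Period. It then makes an exception for tests: "They will only be performed if any clinically significant imbalances between study groups appear to be of major importance for the interpretation" of the primary result, and says that these imbalances "need to be cautiously examined in order to determine whether the randomisation has failed or not".

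The next sentence has a looser trigger: "If this descriptive analysis provides any clues on potential imbalances, further statistical investigations will be carried out using homogeneity tests". If necessary, the adjusting strategy is then redefined and the factor joins those listed in 7.B.3.5. The additional analyses in 7.B.3.5 repeat this for a random imbalance of clinical significance: "this list of a priori identified potentially predictive factors will be implemented accordingly".

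The variables described by group include "the patient's self-evaluations, the severity of dyspnoea", and the data set is the ITT set. On error rates, 7.B says that "the statistical significance level of the various two-sided tests performed will be 5.0" per cent, and "No adjustment for multiplicity will be made".

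**The concern.** A homogeneity test asks whether two samples could come from one population. Whether the randomisation worked is a different question: was each patient given the group that the pre-specified list assigned (4.B.2)? When the list was followed, the null hypothesis is true for Visit 0 variables in all randomised patients, and a small p-value says nothing about the allocation process.

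Two features of this trial make the result still harder to read. The ITT set holds only patients who entered the Follow-Up Period (7.B.3.1). The SGRQ-C, 15D, HADS and dyspnoea scale are first taken at Visit 1 (4.B.3.1), after the Intervention group alone has had four home sessions.

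At stake are a clinical study report that may call a sound randomisation failed, and a factor list that depends on the group comparison. The by-group look also seems to come late: the description at the preliminary lock is global (7.A), and the statistical analysis follows the final lock (7.B).

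**Working it through.** The protocol gives no false-alarm rate for this step, so none can be reproduced. The group sizes used below do reproduce. With P(X<Y) = Φ(10/(25√2)) = 0.611, Noether's formula for the Wilcoxon test gives 142 per group against the stated 143, and 143/(1 − 0.0625) = 152.5, rounded up to 153 (7.B.2).

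**Step 1. What a rejection can mean**

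| Variables and patients | Possible sources of a difference when the list was followed |
|---|---|
| Visit 0 variables, all randomised patients | Chance |
| Visit 0 variables, ITT set | Chance, or selective loss before the end of Visit 1 |
| Variables first measured at Visit 1, ITT set | Chance, selective loss, or an early effect of the home sessions |

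Selective loss is plausible: refusing or being unable to follow the home sessions is a discontinuation reason for the Intervention group only, and patients who stop before the end of Visit 1 are replaced (3.D). In no row does a rejection point to a failed list.

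**Step 2. Chance of at least one p < 0.05 under correct randomisation**

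Inputs: 5% per test and no multiplicity adjustment (7.B). The number k of eligible variables is not stated; 7.B.3.2 lists 15 groups of variables, most with several items. I assume k = 3 to 5 for a strict reading of the trigger and 20 to 30 for a loose one. For independent variables the chance is 1 − 0.95^k:
- k = 3: 1 − 0.857 = 0.143
- k = 5: 1 − 0.774 = 0.226
- k = 20: 1 − 0.358 = 0.642
- k = 30: 1 − 0.215 = 0.785

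For equally correlated normal variables (100,000 simulated sets), k = 20 and 30 give 0.539 and 0.664 at correlation 0.3, and 0.419 and 0.506 at correlation 0.5.

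**Step 3. Picking by eye before testing**

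At 153 per group the standard error of a standardised difference is √(2/153) = 0.114, so p = 0.05 falls at 1.96 × 0.114 = 0.224. Under chance alone a difference of at least 0.15 occurs with probability 0.190, and 0.05/0.190 = 26% of the tests then run are significant. For a visual threshold of 0.20 the share is 0.05/0.080 = 62%. These thresholds are assumptions; the protocol gives none.

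**Step 4. A variable first measured at Visit 1**

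Suppose that the home sessions have already improved SGRQ-C by 4 or 8 points, the protocol's own benchmarks for a slight and a moderate effect (6.A.2.4). The SD is not in the protocol; I assume 16 to 20, with 143 per group. SE = SD × √(2/143) = 1.89 to 2.37, and power is Φ(difference/SE − 1.96):
- 4 points: Φ(0.15) to Φ(−0.27), i.e. 56% to 39%
- 8 points: Φ(2.27) to Φ(1.42), i.e. 99% to 92%

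An early programme effect of that size would often be flagged as an imbalance although the randomisation was sound.

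**Step 5. Effect on the adjusted analysis**

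Simulation of 3,000 trials: 153 per group, no treatment effect, 20 independent normal covariates measured before treatment, ten of them prognostic, normal outcome.
- At least one flagged factor: 65% of trials. At least one flagged factor that also passes a 0.10 outcome screen: 36%.
- Type I error for the group effect: 4.9% unadjusted, 4.1% adjusting for flagged factors, 4.8% adjusting for the ten prognostic factors fixed in advance.
- SD of the estimated group effect: 0.1364, 0.1316 and 0.1164. Choosing by imbalance costs 0.1316/0.1164 = 1.13, about 13% in SD, against pre-specification. That comparison favours pre-specification, since the fixed set is exactly the right one.

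**The case against.** The protocol is more careful than a quick reading suggests, and most of the defence stands.

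- *Testing is the exception.* Systematic tests are barred, and the first trigger demands clinical significance and major importance for the primary result. A reader might infer that everything tabulated will be tested and take 64–79% as the false-alarm rate. The text does not support that: with 3 to 5 eligible variables the figure is 14–23%, and overlapping measures such as FEV1, walking distance and oxygen need lower it for longer lists. Even so, the second trigger is any clue, and no number or threshold is fixed.
- *Not every rejection is a chance finding.* A reader might infer that each one is a false alarm. That is exact only for Visit 0 variables in all randomised patients. In the ITT set a difference may be real and due to selective loss, which is worth knowing but is not failed randomisation.
- *The p-value does not choose the final model.* An added factor is a candidate and must still pass an outcome regression and backward elimination, both at 0.10. That is correct. The candidate list still depends on the observed imbalance.
- *The word random in 7.B.3.5* could be read as excluding differences caused by the programme. But 7.B.3.2 carries no such limit, and neither section says how to tell the two apart.
- *Part of the remedy is there.* Respiratory assistance at Selection and smoking status are pre-listed, the latter as recorded at Visit 1.

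**Conclusion.** The point holds, at low severity. As written, 7.B.3.2 gives homogeneity tests a task that they cannot perform, and lets noticed imbalances extend the factor list, possibly with a variable measured after the home sessions.

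The chance of at least one significant difference under correct randomisation exceeds 5% whenever more than one variable is eligible. Its size, from about 14% to 79% over the cases shown, rests on assumed numbers of variables and correlations. The SGRQ-C figures rest on an assumed SD and a hypothetical Visit 1 effect.

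A reader might go further and infer that the trial's main conclusion is at risk. The protocol does not support that. The primary analysis is an unadjusted Wilcoxon test (7.B.3.5), the regression is exploratory, and 7.B calls all other results descriptive. Nor is inflated type I error shown: the simulation gave 4.1%, though only for covariates measured before treatment. The harm is confined to a possible wrong statement that the randomisation failed and to an exploratory model that is data-driven, less precise than a pre-specified one, and open to adjusting away part of an early programme effect.

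**What to change.** In 7.B.3.2:
- Delete the homogeneity tests and the words about deciding whether the randomisation failed.
- State that randomisation is verified by checking the IVRS allocations against the pre-specified list.
- Describe the balance of Visit 0 variables by group without tests, on all randomised patients as well as on the ITT set, so that loss before the end of Visit 1 can be seen.

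In 7.B.3.5:
- Fix the candidate covariates in advance on prognostic grounds, including the stratification factors (centre, smoking status, respiratory assistance) as recorded at Visit 0.
- Replace the sentence that extends the list with one saying that no factor is added because of an observed imbalance, or from measurements first taken at Visit 1 after the home sessions.
- Decide at the same time whether the pre-listed baseline BODE index stays, since it contains the Visit 1 dyspnoea score (6.A.2.6).

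The cost is a few sentences, one extra descriptive table and a check of the allocation list. No new data are needed, and the planned testing is reduced.

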#### 7.B.3.3. Handling of dropouts and missing data

The number and percentage of patients prematurely withdrawn from the study after their randomisation will be provided by study group (*and globally*) for all randomised patients (*i.e., on the FAS defined in section 7.B.3.1*), as well as for the subgroup of randomised patients having entered the *Follow-Up Period* (*i.e., on the ITT data set defined in section 7.B.3.1*). All withdrawn patients after randomisation will be further described by study group (*and globally*) regarding their time to dropout and reason for premature withdrawal. Particular attention will be paid to the description of Adverse Events (*either serious or not serious, according to their regulatory definition provided in section 8.A*) leading to study premature withdrawal, as detailed in section 7.B.3.7.

Time to dropout for any reason (*expressed in number of days*) throughout the *Follow-Up Period* will be described by study group, on the ITT data set, using Kaplan-Meier's estimates. It will be compared between both study groups with the Log rank test.

Moreover, time to death whatever its associated diagnosis (*expressed in number of days*) throughout the *Follow-Up Period* will be described by study group, on the ITT data set, using Kaplan-Meier's estimates. If relevant, it will be compared between both study groups with the Log rank test.

If relevant, the handling of missing data and/or mistimed evaluations will be described in the statistical analysis plan approved prior to the database lock. Whenever needed, the most pragmatic approach will be used to extrapolate missing information according to the Intention To Treat principles.

